#### 14.4 Monitoring

The sponsor will use a combination of remote and on-site monitoring to monitor this trial. The sponsor or delegate will perform on-site monitoring visits as frequently as necessary. The monitor will record dates of the visits in a trial site visit log that will be kept at the trial site. The first post-initiation monitoring visit will be made as soon as possible after enrollment (ie, the first subject has signed the ICF) has begun. At these visits, the monitor will compare the data entered into the eCRFs with the hospital or clinic records (source documents). The nature and location of all source

Version: 4.0

documents will be identified to ensure that all sources of original data required to complete the eCRF are known to the sponsor and trial-site personnel and are accessible for verification by the sponsor trial-site contact. If electronic records are maintained at the trial site, the method of verification must be discussed with the trial-site personnel. Where allowed in accordance with local regulations, eg, in the event of a national emergency, and in agreement with the investigator, remote source data verification or source data review may be performed.

The investigator must permit the monitor access to all source data, including electronic medical records, and/or documents with the purpose of verifying that the data recorded in the eCRF are consistent with the original source data. Findings from this review of eCRFs and source documents will be discussed with the trial-site personnel. The sponsor expects that, during monitoring visits, the relevant trial-site personnel will be available, the source documentation will be accessible, and a suitable environment will be provided for review of trial-related documents. The monitor will meet/talk with the investigator on a regular basis during the trial to provide feedback on the trial conduct.

In addition to on-site monitoring visits, remote contacts can occur. It is expected that during these remote contacts, trial-site personnel will be available to provide an update on the progress of the trial at the site.

# 14.5 On-Site Audits

Representatives of the sponsor's clinical quality assurance department may visit the trial site at any time during or after completion of the trial to conduct an audit of the trial in compliance with regulatory guidelines and company policy. These audits will require access to all trial records, including source documents, for inspection and comparison with the eCRFs. Subject privacy must, however, be respected. The principal investigator and trial-site personnel are responsible for being present and available for consultation during routinely scheduled trial-site audit visits conducted by the sponsor or its designees.

Similar procedures for inspections may also be conducted by agents of any regulatory body, either as part of a national GCP compliance program or to review the results of this trial in support of a regulatory submission. The investigator should immediately notify the sponsor if he or she has been contacted by a regulatory agency concerning an upcoming inspection. Regulatory Inspectors must be allowed direct access to original medical records (source data/documents).

#### 14.6 Publication Policy

All information, including but not limited to information regarding GEN1044 or the sponsor's operations (eg patent application, formulas, manufacturing processes, basic scientific data, prior clinical data, formulation information) supplied by the sponsor to the investigator and not previously published, and any data, including exploratory or biomarker research data, generated as a result of this trial, are considered confidential and remain the sole property of the sponsor. The investigator agrees to maintain this information in confidence and use this information only to accomplish this trial, and will not use it for other purposes without the sponsor's prior written consent. CROs involved in the trial are not permitted to publish without the sponsor's prior written approval.

The investigator understands that the information developed in the trial will be used by the sponsor in connection with the continued development of GEN1044, and thus may be disclosed as required to other clinical investigators or regulatory agencies. To permit the information derived from the

Version: 4.0

clinical trials to be used, the investigator is obligated to provide the sponsor with all data obtained in the trial.

The results of the trial will be reported in a CSR generated by the sponsor and will contain data from all trial sites that participated in the trial. Recruitment performance or specific expertise related to the nature and the key assessment parameters of the trial will be used to determine a coordinating investigator for the CSR (eg, when a signature by a coordinating investigator is required). Results of exploratory biomarker analyses performed after the CSR has been issued will be reported in a separate report and will not require a revision of the CSR. Trial subject identifiers will not be used in publication of results. Any work created in connection with performance of the trial and contained in the data that can benefit from copyright protection (except any publication by the investigator as provided for below) shall be the property of the sponsor as author and owner of copyright in such work.

Consistent with Good Publication Practices and International Committee of Medical Journal Editors guidelines (Battisti et al., 2015; ICMJE, 2010; ICMJE, 2019), the sponsor in conjunction with any collaborative group(s), shall have the right to publish such primary (multicenter) data and information as per the pre-specified and approved publication plan. If an investigator wishes to publish information from the trial, a copy of the manuscript must be provided to the sponsor for review at least 60 days before submission for publication or presentation. Expedited reviews will be arranged for abstracts, poster presentations, or other materials. If requested by the sponsor in writing, the investigator will withhold such publication for up to an additional 60 days to allow for filing of a patent application. In the event that issues arise regarding scientific integrity or regulatory compliance, the sponsor will review these issues with the investigator. The sponsor will not mandate modifications to scientific content and does not have the right to suppress information. For multicenter trial designs and sub-trial approaches, secondary results generally should not be published before the primary endpoints of a trial have been published. Similarly, investigators will recognize the integrity of a multicenter trial by not submitting for publication data derived from the individual trial site until the combined results from the completed trial have been submitted for publication, within 12 months of the availability of the final data (tables, listings, graphs), or the sponsor confirms there will be no multicenter trial publication.

Authorship of publications resulting from this trial will be based on the guidelines on authorship, such as those described in the current version of 'Recommendations for the Conduct, Reporting, Editing and Publication of Scholarly Work in Medical Journals' (ICMJE Recommendations) http://www.icmje.org/recommendations/), which state that the named authors must have made a significant contribution to the design of the trial or analysis and interpretation of the data, provided critical review of the paper, given final approval of the final version, and agreed to be accountable for all aspects of the work.

#### 14.7 Registration of Clinical Trials and Disclosure of Results

It is the responsibility of Genmab to register the trial in an appropriate public registry according to applicable regulations (eg, www.ClinicalTrials.gov; a website maintained by the National Library of Medicine at the US National Institutes of Health; trial registration may occur in other registries in accordance with local regulatory requirements). A summary of the trial results is made publicly available in accordance with applicable regulatory requirements.

Version: 4.0

# 14.8 Liabilities and Insurance

The sponsor is responsible for taking out relevant clinical trial insurance in accordance with local law and regulations.

Genmab

### **Appendix 1 Definition of Reproductive Potential and Contraception**

In this trial, subjects are considered to have reproductive potential, unless they are postmenopausal or permanently sterile.

- A postmenopausal state is defined as no menses, in subjects >45 years of age, for 12 months without an alternative medical cause. A high follicle-stimulating hormone (FSH) level in the postmenopausal range may be used to confirm a post-menopausal state in subjects not using hormonal contraception or hormonal replacement therapy. However, in the absence of 12 months of amenorrhea, a single FSH measurement is insufficient.
- Permanent sterilization methods include hysterectomy, bilateral salpingectomy and bilateral oophorectomy.

All female subjects must agree not to donate eggs (ova, oocytes) for the purpose of assisted reproduction during the trial and for 4 months after receiving the last dose of GEN1044.

Female subjects of reproductive potential must agree to use adequate contraception during and for 4 months after the last GEN1044 administration. Adequate contraception is defined as highly effective methods of contraception (Table 22). Birth control methods are considered highly effective if they have a failure rate of less than 1% per year, when used consistently and correctly.

### **Table 22 Highly Effective Methods of Contraception**

- Combined (estrogen and progestogen containing) hormonal contraception associated with inhibition of ovulation:
  - Oral
  - Intravaginal
  - Transdermal
- Progestogen-only hormonal contraception associated with inhibition of ovulation:
  - Oral
  - Injectable
  - Implantable
- Intrauterine device
- Intrauterine hormone-releasing system^2
- Bilateral tubal occlusion
- Vasectomized partner
- Sexual abstinence
- 1 Hormonal contraception may be susceptible to interaction with GEN1044, which may reduce the efficacy of the contraception method.
- 2 Contraception methods that, in the context of this guidance, are considered to have low user dependency.
- 3 Vasectomized partner is a highly effective birth control method provided that partner is the sole sexual partner of the female subject of child-bearing potential (ie, the trial subject) and that the vasectomized partner has received medical assessment of the surgical success.
- 4 In the context of this guidance, sexual abstinence is considered a highly effective method only if defined as refraining from heterosexual intercourse during the entire period of risk associated with the trial treatment. The reliability of sexual abstinence needs to be evaluated in relation to the duration of the clinical trial and the preferred and usual lifestyle of the subject.

Table adapted from 'Recommendations related to contraception and pregnancy testing in clinical trials, version 1.1. (CTFG, 2020).

Version: 4.0

## Appendix 2 RECIST (Version 1.1) Criteria Summary

Respon	Response Evaluation Criteria in Solid Tumors (RECIST) 1.1			
Term	Definition			
Complete response (CR)	All of the following:  • Disappearance of all target and non-target tumor lesions  AND  • Reduction in short axis to <10 mm in all pathological target and non-target lymph nodes*			
	AND     Normalization of tumor marker level (if applicable)			
Partial response (PR)	Normanization of tumor marker lever (if applicable)      30% decrease in the sum of diameters of target lesions, taking as reference the baseline sum diameters.			
Progressive disease (PD)	At least one of the following:  • ≥20% increase in the sum of diameters of target lesions, taking as reference the smallest sum on study (nadir; this includes the baseline sum if that is the smallest on study) AND an absolute increase of ≥5 mm in the sum of diameters  OR  • Unequivocal† appearance of 1 or more new lesion(s)  OR  • Unequivocal progression of non-target lesions‡			
Stable disease (SD)	Neither sufficient shrinkage to qualify for PR nor sufficient increase to qualify for PD, taking as reference the smallest sum diameters (nadir) while on study.			

**Note:** A measurable lesion must be accurately measured in at least 1 dimension (longest diameter in the plane of measurement is to be recorded) with a minimum size of 10 mm by CT scan (CT slice thickness no greater than 5 mm).

A response (CR or PR) will be considered confirmed if the following response assessment (4-6 weeks after the initial response) still shows response (CR or PR). In cases where the initial response is followed by SD, it will be considered as confirmed if the SD is later followed by PR or CR. For example, if a patient had PR in week 6, SD in week 12, and PR in week 18, this PR will be considered as confirmed.

\* When lymph nodes are included as target lesions, the sum of lesions may not reach 0 mm even if CR criteria are met, since a normal lymph node is defined as having a short axis <10 mm.

† Not attributable to differences in scanning technique, change in imaging modality, or findings thought to represent something other than tumor (healing or flare of pre-existing lesions).

‡ Modest increases in the size of one or more non-target lesions are not considered unequivocal progression. From RECIST version 1.1 (Eisenhauer et al., 2009).

Version: 4.0

## **Appendix 3 Corticosteroid Dose Equivalents**

Steroid	Approximate Equivalent Dose	
Betamethasone	12 mg	Long-acting
Dexamethasone	15 mg	Long-acting
Methylprednisolone	80 mg	Intermediate-acting
Triamcinolone	80 mg	Intermediate-acting
Prednisone	100 mg	Intermediate-acting
Prednisolone	100 mg	Intermediate-acting
Hydrocortisone	400 mg	Short acting
Cortisone	500 mg	Short-acting

Document Number: TMF-34513

Version: 4.0

## Appendix 4 Estimation of Glomerular Filtration Rate Using Cockroft-Gault Formula

Glomerular filtration rate (GFR) may be estimated using the Cockroft-Gault formula

$$GFR = \frac{(140 - age) \times weight \times F_S}{Serum Creatinine \times 72}$$

Units: GFR [mL/min], age [years], weight [kg], serum creatinine [mg/dl],  $F_S$  is a correction Factor for Sex: in males  $F_S = 1$ , in females  $F_S = 0.85$ 

Version: 4.0

# Appendix 5 Prostate Cancer Clinical Trials Working Group 3 Recommendations - Assessment of Bone Lesions in Patients with Prostate Cancer

Adapted from (Scher et al., 2016)

Assessment of bone disease will be done by whole-body radionuclide bone scan. A bone scan will consist of 5 regions including skull, thorax, spine, pelvis, and extremities. Radiographic progression for bone disease will be assessed using the PCWG3 recommendations (Scher et al, 2016).

Table 23 Standard Baseline Disease Imaging Assessment of the Bone (Prostate Cancer Only)

Assessment		
Imaging	Bone	99m Tc-methylene diphosphonate ( 99m TcMDP) bone scan:
		
 
Record bone lesions and sites of bone lesions
 

Source: From Table 2, Scher et al., 2016

Table 24 Criteria for Progression of Bone Lesions (Prostate Cancer Only)

Assessment		
Imaging	Bone	• Two new lesions
		
 
Confirm ambiguous results by other imaging modalities (eg, CT or MRI); note: only positivity on the bone scan defines metastatic
 

		disease to bone

Source: From Table 3, Scher et al., 2016

Version: 4.0

Table 25 Prostate Cancer: Overall Combined PCWG3-Modified RECIST 1.1 Response

RECIST 1.1 response	PCWG3 response	PCWG3-modified RECIST 1.1	
PD	Any	PD	
Any	PD	PD	
Any (except PD)	PDu	PDu	
NE	Non-PD, NED, or NE*	NE	
SD	Non-PD, NED, or NE*	SD	
Non-CR/Non-PD	Non-PD, NED, or NE*	Non-CR/Non-PD	
PR	Non-PD, NED, or NE*	PR	
CR	Non-PED or NE*	PR (if target lesions at baseline)	
		OR	
		Non-CR/Non-PD (if no target lesions at baseline)	
CR	NED	CR	
Any	Not evaluated	RECIST v1.1	

NE=non-evaluable (scan quality, missing, etc); NED=no evidence of disease; PDu=unconfirmed disease progression.

\* If the bone scan is entirely missing or was not done, and bone lesions were present at baseline, the overall combined PCWG3-modified RECIST 1.1 response is NE.

Version: 4.0

## Appendix 6 Management of Cytokine Release Syndrome

Table 26 Management of Cytokine Release Syndrome

CRS Grade	Management
1	Fever: Patients with a new fever should be admitted to the hospital if not already. Investigate for infection and rapidly startup broad-spectrum antibiotics. Continuation of antibiotic therapy is recommended until any potential neutropenia resolves. Constitutional symptoms may be helped by NSAIDs.
	Tocilizumab: No*.
	Steroids: No.
2	Fever: As per grade 1.
	Hypotension : Immediate clinical evaluation and intervention is warranted. At the first confirmed decrease $\geq$ 20% from baseline systolic, diastolic, or mean arterial pressure or evidence of worsening perfusion, administer an IV fluid bolus (20 mL/kg up to 1 L). Consider a vasopressor and administer no later than after the 3 rd IV fluid bolus due to the vasodilation and capillary leak associated with CRS.
	Hypoxia : Consider X-ray or CT-scan if hypoxic and/or tachypneic. Administer oxygen by low-flow nasal cannula (≤6 L/min) or blow-by.
	Tocilizumab: No* (yes, if the patient has comorbidities†).
	Steroids : No (consider, if the patient has comorbidities‡).
3	Fever: As per grade 1.
	Hypotension : Immediate clinical evaluation and intervention is warranted. Administer a vasopressor (norepinephrine), with or without vasopressin, as most patients with CRS have peripheral vasodilation.
	Hypoxia : Administer oxygen by high-flow nasal cannula (>6 L/min), facemask, non-breather mask, or Venturi mask.
	Tocilizumab: Yes†.
	Steroids: Consider‡.
4	Fever: As per grade 1.
	Hypotension : Immediate clinical evaluation and intervention is warranted. Administer at least 2 vasopressors, with or without vasopressin, as most patients with CRS have peripheral vasodilation.
	Hypoxia: Administer positive pressure (eg, CPAP, BiPAP, intubation, and mechanical ventilation).
	Tocilizumab: Yes†.
	Steroids: Yes ‡ .

- \* Consider earlier intervention in specific cases. For example, an elderly patient with prolonged (>72 hours) and/or very high (>40.5°C/104.9°F) fever may not tolerate the resulting sinus tachycardia as well as a younger patient, so tocilizumab may be indicated.
- † Tocilizumab (anti-IL-6R mAb) remains the only first-line anti-cytokine therapy approved for CRS. If there is no improvement in symptoms within 6 hours, or if the patient starts to deteriorate after initial improvement, a second dose of tocilizumab should be administered along with a dose of corticosteroids. For patients being refractory to tocilizumab (3 administrations), additional cytokine blockade therapy such as siltuximab (anti-IL-6 mAb) or anakinra (anti-IL-1R mAb) may be considered. However, such use is anecdotal and has low level of evidence and, as such, is entirely at the discretion of the treating physician.
- ‡ Consider dexamethasone over methylprednisolone due to improved CNS penetration even in absence of neurotoxicity, as high-grade CRS is correlated with risk of concurrent or subsequent immune effector cell-associated neurotoxicity syndrome (ICANS). If concurrent ICANS is observed, dexamethasone should be preferred.

Source: (Varadarajan et al., 2020)

Version: 4.0

## **Appendix 7 Dose Modification Guidelines for Specific Adverse Events**

**Table 27 Dose Modification Guidelines for Specific Adverse Events** 

System	Adverse Event(s)	Toxicity Grade or Condition (CTCAE v5.0)	Action to be Taken With GEN1044	Adverse Event Management
Immune system disorder	Cytokine release syndrome or ICANS	Grade 3 and cytokine blockade- refractory** for >72 hours	Permanently discontinue	
	CRS or ICANS	Grade 4	Permanently discontinue	
Hepatic	AST/ALT elevation or increased bilirubin	Grade 2; first occurrence	Withhold*	Administer corticosteroids (initial dose of 0.5 to 1 mg/kg prednisone or equivalent) followed by taper.
		Grade 2; second or following occurrence	Withhold*	Administer corticosteroids (initial dose of 0.5 to 1 mg/kg prednisone or equivalent) followed by taper.
		Grade 3; first occurrence	Withhold*	Administer corticosteroids (initial dose of 0.5 to 1 mg/kg prednisone or equivalent) followed by taper.
		Grade 3; second occurrence	Permanently discontinue	
		Grade 4; first occurrence (not recurrent)	Permanently discontinue	
Hematological	Platelet count decreased/	Grade ≥3; first occurrence	Withhold*	Platelet infusions may be administered per institutional standards.
	thrombocytopenia	Grade ≥3; second occurrence	Permanently discontinue	
	Neutropenia	Grade 2; first occurrence	Withhold*	Growth factors may be administered per institutional standards.
		Grade 2; second or following occurrence	Withhold*	Growth factors may be administered per institutional standards.
		Grade ≥3; first occurrence	Withhold*	Growth factors may be administered per institutional standards.
		Grade ≥3; second occurrence	Permanently discontinue	
	Febrile neutropenia	Grade ≥3; first occurrence	Withhold*	Growth factors may be administered per institutional standards.
		Grade ≥3; second occurrence	Permanently discontinue	

Version: 4.0

System

Adverse Event(s)
Condition
(CTCAE v5.0)

Gastrointestinal

Nausea and/or vomiting >72 hours

Condition
(CTCAE v5.0)

Grade 2; first occurrence

Withhold\*
Prophylactic administration of antiemetic therapy may be administered per institutional standards.

Conde 2: record on Withhold\*

[figure not shown]
Prophylactic administration of antiemetic therapy may be administered per institutional standards.

	l	(= = .000)		
Gastrointestinal	Nausea and/or vomiting >72 hours	Grade 2; first occurrence	Withhold*	Prophylactic administration of antiemetic therapy may be administered per institutional standards.
		Grade 2; second or following occurrence	Withhold*	Prophylactic administration of antiemetic therapy may be administered per institutional standards.
		Grade ≥3; first occurrence	Withhold*	Prophylactic administration of antiemetic therapy may be administered per institutional standards.
		Grade ≥3; second occurrence	Permanently discontinue	
	Diarrhea >72 hours	Grade 2; first occurrence	Withhold*	If the diarrhea is of immune-related etiology, administer corticosteroids (initial dose of 1-2 mg/kg prednisone or equivalent) followed by taper.
		Grade 2; second or following occurrence	Withhold*	If the diarrhea is of immune-related etiology, administer corticosteroids (initial dose of 1-2 mg/kg prednisone or equivalent) followed by taper.
		Grade ≥3; first occurrence	Withhold*	If the diarrhea is of immune-related etiology, administer corticosteroids (initial dose of 1-2 mg/kg prednisone or equivalent) followed by taper.
		Grade ≥3; second occurrence	Permanently discontinue	
Other non-hematologic		Grade 3; first occurrence	Withhold*	
G		Grade 3; recurrent	Permanently discontinue	
	1	Grade 4; first	Permanently	

\* GEN1044 can be resumed after AE has resolved to grade ≤1 and corticosteroid has been tapered. If GEN1044 is held for more than 12 weeks, the subject should be permanently discontinued from therapy.

\*\* Including adequate and repeated treatment (3 doses within 24 hours) with anti-IL-6R mAb (tocilizumab). **Note:** For dose escalation, these rules will only apply to the post-DLT period.

## **Appendix 8 Recommended ICANS Management**

Source: (Garcia Borrega et al., 2019; Lee et al., 2019)

<sup>2 Borrega Garcia et al., 2019.

Version: 4.0

## Appendix 9 Description of DLT Rates After Protocol Amendment 3

Table 28 Dose-Determining Analysis Sets Comparison

DLT Consideration	Number FAS	Number DLT Evaluable	DLT Period	Comment
DL cohort	All those with at least 1 dose (ie, prime dose) administered	All those who meet the exposure criteria for the DL cohort, or experience a DLT during the DLT period	Up to 7 days past 1 st full dose administration	Regardless of what individual dose that the DLT could be associated with, the DLT is attributed to DL cohort as such
Period-specific DLT rates	All those administered the period-specific dose	All those administered the period-specific dose in a timely fashion	Up to 7 days past dose administration	

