**Table 11 Modified BOIN Recommendations** 

	Total Number of DLT Evaluable Subjects Treated on a DL Cohort	3	4	5	6	7	8	9
Recommendation	Escalate	0	0	≤1	≤1	≤1	≤1	≤2
Based on Total Number of DLTs on the DL Cohort	Remain	1	1	-	2	2	2	3
	De-escalate	2	2	2	3	3	3	4
	Terminate a dose level	3	≥3	≥3	≥4	≥4	≥4	≥5

DL=dose level; DLT=dose-limiting toxicity.

Version: 4.0

The DLT rate per each period-specific dose level may be provided to the DEC (supplementary to the DLT rate of the DL cohort) when the DEC is considering the dosing sequence of the next DL cohort. The mBOIN recommendation for the period-specific dose level may be interpreted in the context of Table 11 above (modified mBOIN recommendations). For example, the DLT rate of 3 mg when administered as priming dose will be provided, as will the DLT rate of 3 mg when provided as intermediate dose.

Given the different perspectives the different DLT rate estimates provide, the DEC will evaluate all available data to recommend the doses for the next DL cohort; the Safety Committee will make the final decision. A template for DLT reporting is provided in Appendix 9, Table 29.

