### Dose Level Termination:

A potential drawback of the basic BOIN design is that, theoretically, a "very toxic" DL cohort could be investigated in multiple cohorts, if a neighboring DL cohort is not toxic. To avoid this problem, a dose level termination criterion is implemented (for DL cohorts with at least 3 DLT evaluable subjects): A DL cohort can no longer be investigated if an additional DLT-free cohort would lead to de-escalation.

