#### 11.1.7 Dose-Determining Analysis Set – Dose Escalation Part

The dose-determining set (DDS), which is used to define the number of DLT evaluable subjects on a DL cohort, will include all FAS subjects in the escalation part who meet the exposure criterion (defined below) and have sufficient safety evaluations, or experience a DLT prior to the 2nd full dose administration. The DLT period will extend until 7 days after the first full dose (see Section 4.2).

A subject meets the exposure criterion if all doses, up to and including the 1st full dose, are administered in a timely fashion: In general, the individual doses should not be delayed more than 7 days. However, longer dose delays might be acceptable if the DEC considers the assessments still to be appropriate. The first full dose should be administered at latest by 30 calendar days after C1D1 (if one intermediate dose is administered), or by 38 calendar days after C1D1 (if two intermediate doses are administered), counting the day of first exposure as C1D1.

If there is a longer dose delay the subject is considered as non-DLT evaluable (as long as the reason for the dose delay, or the dose delay itself, is not classified as a DLT). DLTs occurring beyond the DLT period will be presented, but not contribute to the DLT rates for the DL cohort per mBOIN.

Subjects who do not experience a DLT will be considered to have sufficient safety evaluations if they have been observed for  $\ge 21$  days (or  $\ge 28$  days if 2 intermediate doses are applied) following the priming dose, and are considered by both the sponsor and investigators to have enough safety data to conclude that a DLT did not occur.

For a period-specific dose level (doses up to and including 1st full dose), a subject is considered as DLT evaluable if the dose was timely administered (ie, not delayed for more than 7 days) and had sufficient safety evaluations up to the subsequent dose administration to conclude if a DLT did occur or not. The relative DLT periods for priming and intermediate doses extend the planned timing of the subsequent dosing (ie, extends until 7 days after the dose administration). For the 1st full dose, it extends up to 7 days past drug administration. Appendix 9 provides a comparison of the DDS considerations and a template for the reporting of DLT rates.

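### Table 28 leaves out the safety-evaluation condition that Section 11.1.7 sets for DLT-evaluable subjects; applied as written, it can only lower the DLT rate

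*Protocol*

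**What the plan says.** Protocol Section 11.1.7 defines who is DLT-evaluable. The dose-determining set takes escalation subjects who "meet the exposure criterion (defined below) and have sufficient safety evaluations, or experience a DLT prior to the" second full dose. Exposure is a matter of dosing only: "A subject meets the exposure criterion if all doses, up to and including the 1 st full dose, are administered in a timely fashion". Safety evaluation is a separate test for subjects without a DLT. They need at least 21 days of observation from the priming dose (28 with two intermediate doses), and the sponsor and investigators must agree that the data suffice to rule out a DLT. For a period-specific dose, the dose must be on time and the subject must be one who "had sufficient safety evaluations up to the subsequent dose administration to conclude if a DLT did occur or not".

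Protocol Section 4.2.2 (item 3) and the dose-determining set in SAP Section 4 likewise ask for both exposure and safety evaluation, or a DLT.

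Appendix 9, Table 28 has a column for the number DLT-evaluable. The dose-level cohort entry is "All those who meet the exposure criteria for the DL cohort, or experience a DLT during the DLT period". The period-specific entry is "All those administered the period-specific dose in a timely fashion". Neither mentions safety evaluation. Section 4.2 points to Appendix 9 for the DLT tables given to the Dose Escalation Committee (DEC), and the Table 29 template has the same column. Under Section 4.2.1, cohort counts are read against Table 11, and period-specific counts may be.

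**The concern.** The number evaluable is the denominator of the DLT rate, which is a primary endpoint and the input to the escalation table. Because 11.1.7 keeps exposure and follow-up apart, the exposure criteria named in Table 28 cannot be read as including follow-up.

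The subject on whom the two definitions differ receives every dose through the first full dose on time and then leaves observation within the next 7 days without a DLT, for example by withdrawing or through progression or death from the cancer. Table 28 counts this subject as DLT-free; 11.1.7 does not count the subject at all. In the period-specific row the same gap covers the 7 days after the dose in question.

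Only the denominator can grow, so any resulting error is toward a lower DLT rate and a less cautious action. The week concerned is the subject's first at the full dose.

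**Working it through.** **Inputs.** Section 4.2.1 gives a target DLT rate φ = 0.30, φ1 = 0.6 × 0.30 = 0.18 and φ2 = 1.4 × 0.30 = 0.42, with stated thresholds of 24% and 36%. The Table 11 rows for n = 3 to 9 are "Escalate 0 0 ≤1 ≤1 ≤1 ≤1 ≤2" and "Remain 1 1 - 2 2 2 3". The termination rule in Section 4.2.1.1 is: "A DL cohort can no longer be investigated if an additional DLT-free cohort would lead to de-escalation".

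**Reproducing the plan's figures.**

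- λ1 = ln[(1−φ1)/(1−φ)] / ln[φ(1−φ1)/(φ1(1−φ))] = ln(0.82/0.70) / ln(0.246/0.126) = 0.2365
- λ2 = ln[(1−φ)/(1−φ2)] / ln[φ2(1−φ)/(φ(1−φ2))] = ln(0.70/0.58) / ln(0.294/0.174) = 0.3585

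With d DLTs in n subjects: escalate if d/n ≤ λ1, de-escalate if d/n ≥ λ2, terminate if d/(n+3) ≥ λ2. Every Table 11 cell for n = 3 to 9 is reproduced.

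**Effect of one unfollowed subject.** The 11.1.7 count is d/n and the Table 28 count is d/(n+1). Comparing the actions for n = 3 to 8, these are the only changes:

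| 11.1.7 count | Action | Table 28 count | Action |
|---|---|---|---|
| 1/4 (25.0%) | remain | 1/5 (20.0%) | escalate |
| 2/8 (25.0%) | remain | 2/9 (22.2%) | escalate |
| 2/5 (40.0%) | de-escalate | 2/6 (33.3%) | remain |
| 3/8 (37.5%) | de-escalate | 3/9 (33.3%) | remain |
| 3/5 | terminate | 3/6 | de-escalate |
| 4/8 | terminate | 4/9 | de-escalate |

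**The rule at five evaluable subjects.** Section 4.2.1.1 brings 5 evaluable subjects up to 6, and three of the six rows involve a count of five. In the 1/4 versus 1/5 row, a DLT-free sixth subject gives 1/6 under Table 28 and 1/5 under 11.1.7, and Table 11 escalates on both. If the sixth subject has a DLT, the comparison becomes 2/6 (remain) against 2/5 (de-escalate). The rows ending at nine are not affected.

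**More than one unfollowed subject.** With two, remain becomes escalate at 1/3 versus 1/5, 1/4 versus 1/6 and 2/7 versus 2/9. With three, it does so at 1/3 versus 1/6, 1/4 versus 1/7 and 2/6 versus 2/9.

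**A cohort of three.** Section 4.2.1.1 allows a rate to be estimated from two evaluable subjects only if neither had a grade ≥2 AE in the first 7 days of Cycle 1 or any DLT. Suppose one of three subjects is unfollowed and the other two have no DLT, but one of them had such an AE. Under 11.1.7 two are evaluable and the condition fails. Under Table 28 the cohort reads 0/3, escalate, and the condition is never tested.

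**How common the vulnerable counts are.** At a true DLT rate of 30%, exactly 1 DLT in 4 has probability 4 × 0.3 × 0.7³ = 0.41, and exactly 2 in 8 has 28 × 0.3² × 0.7⁶ = 0.30. At 42% the figures are 0.33 and 0.19. These are probabilities of the counts, not of a changed decision, which also needs an unfollowed subject. The documents give no rate for such loss.

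**The case against.** The strongest reply is that Table 28 does not govern. Section 11.1.7 says that the dose-determining set fixes the number evaluable, and it presents Appendix 9 only as a comparison and a reporting template. Table 28 cannot even be applied alone, because it names exposure criteria that only 11.1.7 defines. Sections 11.1.7 and 4.2.2 and the SAP all carry the condition, so Table 28 reads as an incomplete summary. This stands, and it makes the effect conditional on someone using the shorter definition.

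Three further limits also stand:

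- Loss after a priming or intermediate dose does not matter in the cohort row, because exposure already requires the first full dose. It matters only for the period-specific rates, which are supplementary.
- Under Section 7.1, related toxicity that causes discontinuation in Cycle 1 is itself a DLT, as is any grade 5 toxicity. The gap is therefore mainly loss for other reasons, although the Cycle 1 clause would not reach a first full dose given on Cycle 2 Day 1.
- Table 11 is not automatic. The DEC reviews all available data and the Safety Committee decides.

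A reader might infer that early losses did count as DLT-free in this trial and that escalation was biased upward. The documents do not support that: they do not say which definition produced the DEC tables or how many subjects were lost in that week. What survives is that one protocol gives two different descriptions of the same denominator, and the incomplete one stands beside the template to be filled in.

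**Conclusion.** The inconsistency is real and should be corrected. Its potential effect has one direction and is limited in size. With one misclassified subject, the move from remain to escalate occurs at two counts. Only 2/8 versus 2/9 is untouched by the five-subject rule; 1/4 versus 1/5 is softened by it. The move from de-escalate to remain occurs at 3/8 versus 3/9 and at 2/5 versus 2/6, where the 2/5 count also meets that rule. A cohort of three can bypass the safeguard for two evaluable subjects.

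All of this assumes that Table 28 was used in place of 11.1.7, that a subject was lost without a DLT in the relevant 7 days, and that the committees followed Table 11. It would go too far to say that Table 28 makes subjects evaluable on exposure alone, since the cohort row also admits anyone with a DLT, or that loss after any dose distorts the cohort rate. With enrollment stopped (SAP Section 1.2), what remains is the correctness of the DLT-evaluable counts already reported.

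**What to change.** Align Table 28 with Section 11.1.7:

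- **Dose-level cohort cell:** after the exposure criteria, add that the subject must also have sufficient safety evaluations per Section 11.1.7. Leave the DLT alternative unchanged.
- **Period-specific cell:** after timely administration, add sufficient safety evaluations up to the subsequent dose (7 days) per Section 11.1.7.

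Because enrollment has stopped, the sponsor should also confirm that the DLT-evaluable counts already given to the DEC applied the 11.1.7 condition. Any cohort where they did not should be recounted.

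A separate point to reconcile at the same time is that the SAP's dose-determining set has the safety-evaluation condition but uses a different exposure rule (at least 2 of 3 planned doses, and a fixed 21 days).

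The cost is the wording of two table cells and a check of existing counts. There may be slightly fewer evaluable subjects, which is what 11.1.7 already intends.
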